### Piecewise Exponential (PWE) Survival Model

A constant underlying hazard assumption in each of the periods will be assumed. For the primary outcome analysis through the primary endpoint of 3 to a maximum of 5 years, an interval censored proportional hazard model will be fitted with an assumed underlying piecewise exponential hazard with five constant-hazard periods: [0, 12], (12, 24], (24, 36], (36, 48] and (48, 60] and controlled for randomized surgical intervention, pooled site and age category (<65 and  $\geq$ 65) consistent with study randomization design. If the model does not converge, the choice of period cut points will be evaluated with a plot of the NPMLE survival function (see Nonparametric Survival Analysis for Interval-Censored Data below) and periods will be combined as needed for model convergence while retaining clinical relevance. The PWE survival model will be fit using the SAS ICPHREG procedure.

From this single model, point estimates of the overall adjusted hazard ratios across all time periods along with confidence intervals and p-values corresponding to the 4 a priori specified hypothesis tests comparing risk of surgical failure across the surgical arms are obtained. The log-log transformation will be used to calculate confidence intervals. Specifically, the first test will compare the overall adjusted hazard ratio across all time periods of the transvaginal mesh arm to the mesh augmented sacrocolpopexy arm against the hypothesized non-inferiority margin of 1.93 evaluated at a one-sided significance level of  $\alpha = 0.03$ . The p-value will test if the hazard ratio is not more than 1.93. A corresponding upper 1-sided 97% confidence interval will be provided. The second test is for superiority of transvaginal mesh to mesh augmented sacrocolpopexy arm against the hypothesized null ratio of 1.0 evaluated at a two-sided significance level of  $\alpha = 0.03$ , with corresponding 97% 2-sided confidence interval. While this test will be provided, it is a step-down of the first test, and will be evaluated for statistical significance only if the first test rejects the inferiority null hypothesis. The other two hypothesis tests of superiority will compare the overall adjusted hazard ratio across all time periods of transvaginal mesh and mesh augmented sacrocolpopexy, respectively, to native tissue

repair against the hypothesized null ratio of 1.0 each evaluated at a two-sided significance level of  $\alpha = 0.01$ , and corresponding 2-sided 99% confidence interval. Note that pairwise comparisons will be completed within the model that contains all 3 treatment groups.

In addition, model estimates and 95% confidence intervals for the failure probability in each surgical group will be obtained at years 1, 2, 3, 4, and 5. Model-adjusted hazard rates (estimate and 95% confidence intervals) for each period will be obtained. The hazard rates will be reported as incidence density per person-year for each of the periods. For all estimates and contrasts, pooled sites and age category categories (<65 and  $\geq$ 65) will be given equal weight.

Descriptive statistics for the analysis will also include the number of participants by treatment group censored within each time interval, the median (IQR) follow-up time by treatment group, and the model hazard rate (incidence density per person year) by treatment group within each time interval.

The general structure of the SAS code that will be used for the piecewise model is summarized below.

PROC ICPHREG PLOTS(CL TIMERANGE=(0,60))=(survival) ALPHA=&alpha. NLOPTIONS(MAXIT=500); CLASS treatment; MODEL (LowerboundTIME, UpperboundTIME)= treatment Age\_group poolsite1 poolsite2 poolsite3 poolsite4 poolsite5 poolsite6 / BASE=piecewiseexponential(INTERVALS=(12,24,36,48))/ HAZSCALE=HAZARD; HAZARDRATIO "HR" treatment / DIFF=REFERENCE; TEST treatment / HTYPE=3; BASELINE OUT=work.pwe\_surv\_haz\_estimates COVARIATES=work.pwe\_covs TIMELIST=0 to 60 by 6 SURVIVAL=\_ALL\_ HAZARD= ALL / ROWID=treatment CLTYPE=LOGLOG;

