It is anticipated that subjects will come from the practices of PFDN investigators. Subjects with bothersome prolapse complaints and prolapse beyond the hymen will be offered the range of therapeutic options consistent with the physician's practice including, but not limited to, expectant management, conservative treatment, and abdominal or vaginal surgery for their condition. Those subjects desiring surgery will be offered participation in this trial. The pelvic organ prolapse quantitative exam and a bothersome bulge question (Question 3 of the PFDI-20) are used routinely in clinical care and will be used to determine eligibility.

Objective: Pelvic Organ Prolapse Quantification (POP-Q)

The pelvic organ prolapse evaluation will be performed according to the guidelines established by the International Continence Society. [44] The procedure will be standardized as demonstrated in a DVD produced by Duke University Medical Center ("Pelvic Organ Prolapse Quantification Examination"). Examinations will be performed in the dorsal lithotomy position with the participant straining maximally. Participants will be asked to confirm that the extent of prolapse demonstrated during the examination is consistent with the maximum degree of prolapse seen in their daily life. Standing POP-Q examinations will be performed if maximal prolapse cannot be demonstrated in the dorsal lithotomy position.

Subjective: Participants will be considered as having bothersome vaginal bulge symptoms if they report a positive response to PFDI-20 Question 3 and any degree of bother (i.e. any response other than "not at all" to the question "How much does this bother you?"):

a. Question 3: Do you usually have a bulge or something falling out that you can see or feel in your vaginal area?

G. BASELINE VISIT

Candidates will be approached for enrollment in a manner consistent with local IRB requirements and will be consented and enrolled in the study with verbal and written consent. Once eligibility is confirmed, baseline information will be obtained, which will include Demographics, Medical History, Physical Examination, and baseline patient-reported outcome (PRO) forms.

Demographics and Medical History

- Age, race/ethnicity, marital status, education
- Obstetric history (vaginal parity)
- Prior surgical treatment of pelvic organ prolapse or urinary incontinence
- Estrogen status
- Prior treatment of pelvic organ prolapse or urinary incontinence
- Smoking
- Diabetes

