On April 16, 2019, the FDA ordered the removal of transvaginal mesh products including Uphold LITE from the market. The PFDN Steering Committee, with approval from NICHD and the DSMB, halted study enrollment for new patients and halted randomization into the TVM arm. At the time, there were 344 completed surgeries and 18 remaining consented or randomized participants who were awaiting surgery. Remaining patients that were randomized to TVM will be re-randomized to receive one of the two remaining arms (SC and NT). This randomization will occur in a ratio of 1:1.

Randomization will be performed using permuted blocks with a block size that is known only to the DCC and will be stratified by site and age category (< 65 and \ge 65). For each participant, the web-based system will determine the treatment allocation from a static randomization table developed by the study randomization statistician prior to the start of the study. Only the study statistician and randomization system programmer will have access to the randomization table to minimize the risk of selection bias.

H.2. Masking of Randomized Intervention

The participant will remain masked until after surgical repair. Beginning after April 18, 2019, the pending participants who have not undergone surgery will be notified that they will not be randomized into the TVM arm given that this arm is closed at this time. These participants will remain masked to their surgical randomization (SC and NT) until after their surgical repair. Those participants receiving sacral colpopexy will have abdominal incisions, making masking for this technique impossible. Because masking is impractical for the sacral colpopexy arm, the unmasking of the two vaginal arms will occur postoperatively. Given that the primary outcome is based primarily on outcome measures obtained by a masked examiner, unmasking of the participants should not bias the outcomes.

The study surgeon is providing clinical care to enrolled participants, thus masking the surgeon to treatment allocation or participant symptoms is not practical or feasible, other than the allocation concealment prior to surgical randomization.

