 - (a) Rates of pain captured from the modified Surgical Pain Scale [56], pain medication use (during 24 hours prior to completing Body Part Pain Score), and location of pain with Body Part Pain Score.
- 4. Pelvic infection
 - (a) Perioperative infections
 - (b) Urinary tract infections
 - (c) Vaginal infections with flora uncommon to the vaginal canal
- 5. De novo vaginal bleeding, atypical vaginal discharge, fistula formation, neuromuscular problems (including groin, buttock and leg pain).
- Need for subsequent procedures: any surgical or non-surgical treatment for pelvic floor disorders (including urinary incontinence, voiding dysfunction, defecatory dysfunction, fecal incontinence, recurrent prolapse, and dyspareunia/pelvic pain).
- Rates of vaginal scarring, defined as de novo scar requiring medical or surgical intervention.

8. Rates of vaginal shortening (TVL < 6 cm), de novo dyspareunia, and worsening dyspareunia with AE survey.

Secondary Aim 3 – Predictors of Poor Outcomes: Assess common factors believed to be associated with surgical treatment failures including:

- 1. Advanced prolapse
- 2. Age
- 3. Obesity
- 4. Smoking
- 5. Use of supplemental estrogen
- 6. Previous POP surgery

Secondary Aim 4 – Body Image: Given the concerns with the impact of mesh placement and vaginal prolapse on body image, body image scales will be obtained and compared between groups.

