with the appropriate parametric or nonparametric statistical tests. We will first conduct a model-based analysis using an appropriate proportional hazards model that examines failure risk as a function of randomized treatment arm, with details of the modelling approach specified after masked data review and documented in the statistical analysis plan prior to data unmasking. As specified in the statement of hypotheses and further detailed in the statistical analysis plan, within each analysis population, this single model will be used to generate four hypothesis tests, as applicable. The first test will compare the hazard ratio of the transvaginal mesh arm to the mesh augmented sacrocolpopexy arm against the hypothesized non-inferiority margin of 1.93, followed by a test of superiority if non-inferiority is shown, while the other two hypothesis tests will compare the hazard ratio of transvaginal mesh and mesh augmented sacrocolpopexy, respectively, to native tissue repair against the hypothesized null ratio of 1.0. All model-based analyses will include terms for the stratification parameters used in the randomization.

A number of secondary outcome measures that include both continuous and binary measures will be collected periodically across the study. To account for missing data associated with differential follow-up time associated with the primary design, appropriate model-based approaches (linear mixed models for continuous outcomes and generalized linear models for binary measures) will be used to compare the effects of treatment. The approach for these secondary analyses will be included in the statistical analysis plan.

M.4. Futility/Stopping Rules

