#### **3.1.2** Secondary Objectives

The secondary aims for the ASPIRe study, which will be addressed through specific planned secondary analyses and associated hypothesis tests and treatment effect estimates, are:

- 1. Secondary Efficacy Outcomes: To compare detailed anatomic and comprehensive functional outcomes (including prolapse, urinary, sexual, bowel and health related quality of life (HRQOL) across three methods of vault suspension.
- 2. Safety: To measure and compare safety, adverse events (including mesh erosion and exposure), pain, and need for subsequent procedures across three methods of vault suspension.
- 3. Predictors of poor outcomes: To determine if advanced prolapse, age, obesity, smoking, menopausal status, estrogens, previous prolapse surgery, and physical activity levels, alone or in combination, predict higher treatment failure.
- 4. Body image: To describe changes in body image as measured by a validated scale, the Body Image Pelvic Organ Prolapse Scale (BIPOP). in a group of women undergoing apical repair with and without mesh and to evaluate whether or not changes in sexual function are associated with changes in body image.
- 5. Preference Evaluation: To assess patient and surgeon reasoning for declining participation in the trial. This will be determined by the CONSORT diagram for enrollment.
- 6. Cost- effectiveness: To compare the cost across three methods of vault suspension.
- 7. Global Composite Outcome: To evaluate the development of a valid and reliable Global Composite Outcome that balances adverse events and patient-centered outcomes to anatomic definitions of failure and success.
- 8. Patient Perspective in AE Reporting (PPAR): To evaluate the patient's perspective about adverse events and their role in patient decision-making outcomes. The aims of PPAR include comparing patient versus surgeon rankings of complication grade, outcome, expectedness and seriousness, to estimate the association between patient rankings of AEs

with decision-making and quality of life outcomes, and to determine if their perspective about AEs changes over time.

9. Frailty ASPIRe Study (FASt): To determine the impact of preoperative frailty and mobility on surgical treatment outcomes and postoperative complications of older women following surgical correction of apical pelvic organ prolapse (POP).

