# 9.4.2 Primary Efficacy Analysis: Model-Based Survival Analysis

This model-based approach will serve as the primary analytic method for testing the comparative efficacy of the three strategies for uterovaginal prolapse as it can control for study design and potentially confounding variables. To appropriately account for the interval censored and right censored nature of the primary outcome data, and potential violation of the proportional hazards assumption across the entire follow-up time, while controlling for study design and potentially confounding variables in assessing intervention effects, a piecewise exponential (PWE) survival model will be employed. The PWE survival model is a model in which the time scale is divided into *K* periods and the underlying hazard function, h(t), is assumed to be constant within each period such that  $h(t) = \lambda_k \exp(\beta \mathbf{X})$ , where  $\lambda_k$  is the hazard function for period *k*, and **X** is a matrix of explanatory

variables with vector  $\beta$  coefficients (Breslow 1974). This piecewise approach effectively eliminates the need to specify the distribution of the hazard function and satisfies the proportional hazards assumption if the underlying hazard is constant within each period.

Among subjects who experience a surgical failure, the time to surgical failure (primary outcome) will be interval censored (i.e. lower bound, upper bound where both bounds are non-missing and lower bound < upper bound). Subjects who do not experience a surgical failure will be right censored (i.e. non-missing lower bound and missing upper bound) at their last attended visit. Specifically, the censoring interval for implementation in interval censored analysis will be defined as follows:

- lower bound = number of months (i.e. months as intended the by visit schedule) from the surgical intervention to the *last attended visit where the subject was considered to be not a surgical failure* across all post-operative visits starting at the 6 month visit. As such, subjects who were surgical failures at the 6-month post-operative visit will have a lower bound of 1.5 months corresponding to the 6-week post-operative visit. Based on this definition, the lower bound for the primary endpoint of 3 to a maximum of 5 years can take any of the following values 1.5, 6, 12, 18, 24, 30, 36, 42, 48, 54, or 60 months.

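### The primary survival model adjusts only for site and age although SAP 9.4.2 speaks of potential confounders; adding baseline prolapse extent would be a cheap, modest gain in precision

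*SAP*

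**What the plan says.** SAP 9.4.2 prefers the model-based analysis "as it can control for study design and potentially confounding variables". It then says the piecewise exponential (PWE) model is used "while controlling for study design and potentially confounding variables in assessing intervention effects". The model paragraph narrows this to a fit "controlled for randomized surgical intervention, pooled site and age category", and the SAS code beneath it has only treatment, age group and the pooled-site indicators. That agrees with protocol M.3, "All model-based analyses will include terms for the stratification parameters used in the randomization", and with protocol H.1, where randomisation "will be stratified by site and age category".

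Protocol L.2, Secondary Aim 3, plans to "Assess common factors believed to be associated with surgical treatment failures including" a list that contains advanced prolapse and previous prolapse surgery. Protocol A.2.c also names baseline degree of prolapse. SAP 3.1.2 words the same aim as an open question: "To determine if advanced prolapse, age, obesity, smoking, menopausal status, estrogens, previous prolapse surgery, and physical activity levels" and so on. SAP 3.2 sends that question to a separate manuscript.

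Baseline POP-Q is needed for eligibility (protocol E.1 and Table 5). The baseline history in protocol G includes "Prior surgical treatment of pelvic organ prolapse or urinary incontinence".

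The SAP 9.4.3 sensitivity analyses that change the covariate set drop site and age, add enrolment year, or make site a random effect. None adds baseline prolapse. SAP 9.5.1 and 9.5.2 do include the baseline value as a covariate in the repeated-measures models for secondary outcomes.

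**The concern.** The stated purpose of the model and its specification differ. A reader of 9.4.2 would expect at least one clinical baseline covariate, yet apart from treatment the model holds only the two stratification factors. The baseline counterpart of the POP-Q points that define anatomic failure is left out of the primary analysis, although baseline values are used as covariates for secondary outcomes.

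In a proportional hazards model, omitting a strong baseline predictor pulls the treatment hazard ratio (HR) towards 1. It therefore costs power when the arms truly differ. The tests at stake are sacral colpopexy versus native tissue (H2) and transvaginal mesh versus native tissue (H3), each at two-sided 0.01.

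**Working it through.** **1. Reproduce the plan's power without covariates.**

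Inputs from protocol M.1 and SAP 6: 121 per arm; yearly hazards 0.1116 (mesh arms) and 0.2554 (native tissue); 2-year accrual; 3-year minimum follow-up; 5% yearly loss, so η = −ln 0.95 = 0.0513.

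- Expected events per arm = n · λ/(λ+η) · [1 − (e^(−3(λ+η)) − e^(−5(λ+η)))/(2(λ+η))]. This gives 39.5 (mesh) and 70.8 (native tissue).
- H1 (non-inferiority, one-sided 0.03, margin 1.93): SE = √(2/39.5) = 0.225 and ln 1.93 = 0.6575. Power = Φ(0.6575/0.225 − 1.881) = 85.1%. The plan states 85%.
- H2 and H3: SE = √(1/39.5 + 1/70.8) = 0.1986 and ln(0.2554/0.1116) = 0.828. Power = Φ(0.828/0.1986 − 2.576) = 94.5% (Schoenfeld 96.2%, Freedman 93.8%). The plan states more than 93%.

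The planned power therefore does not depend on any covariate.

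**2. Simulate with and without adjustment.**

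The documents give no prognostic strength, so the following are assumptions: two binary predictors (advanced prolapse 50%, prior repair 40%), with a range of HRs. Marginal 2-year success is held at 80% vs 60%. Each run has two arms of 121, with 6-monthly visits, failures placed at interval midpoints, and yearly constant-hazard pieces. Site and age are left out of both models. There are 5,000 trials per setting (2,000 for HRs 3/2), and the Monte Carlo SE is about 0.3 to 0.6 points.

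| Assumed HRs | H2/H3 unadjusted | H2/H3 adjusted |
|---|---|---|
| 1 / 1 | 95.6% | 95.5% |
| 1.25 / 1.25 | 95.5% | 95.7% |
| 1.5 / 1.5 | 95.1% | 96.0% |
| 2 / 2 | 94.1% | 96.4% |
| 3 / 2 | 92.7% | 97.9% |

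If native tissue reaches 65% success instead of 60%, power goes from 76.1% to 75.8% (HRs 1/1), 76.2% to 78.0% (1.5/1.5) and 72.5% to 78.8% (2/2).

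H1 with equal arms goes from 84.6% to 84.4% (1/1), 84.3% to 83.7% (1.5/1.5) and 83.8% to 83.2% (2/2). There is no gain.

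**3. Cross-check with one continuous predictor.**

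A separate simulation used 2,000 trials per setting and 3-year accrual, with prolapse extent alone at log-HR 0.3, 0.5 and 0.7 per SD. Power for H2 went from 95.8% to 96.8%, 92.7% to 95.9% and 92.8% to 97.6%. With no effect it was 95.8% vs 95.9%.

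The two simulations can be put on one scale through the SD of the binary linear predictor:

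- HRs 2/2: √(0.693²·0.25 + 0.693²·0.24) = 0.49
- HRs 3/2: √(1.099²·0.25 + 0.693²·0.24) = 0.65

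The gains of 2.3 and 5.2 points in step 2 are then in line with the 3.2 and 4.8 points at log-HR 0.5 and 0.7.

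**4. Effect on the margin.**

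The 1.93 comes from 80% vs 65% success at 2 years: ln 0.65/ln 0.80 = 1.93. Solving for the conditional HR that gives the same marginal rates, with a normal covariate at log-HR 0.3, 0.5 and 0.7 per SD, gives 1.95, 1.99 and 2.04. Keeping 1.93 for a covariate-conditional HR is slightly conservative.

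**The case against.** The strongest defence is that adjusting only for the stratification factors is prespecified and consistent across protocol M.3, SAP 7.2, the model text and the code. The first phrase in 9.4.2 says only that the model can control for such variables, which explains why it is preferred to the nonparametric method. Age is itself a listed candidate predictor. The prognostic strength of prolapse extent is an open question in the trial, within a cohort where everyone already has prolapse beyond the hymen. All of this stands, and it keeps the point small. It does not remove the mismatch in the second phrase or the absence of any adjusted analysis.

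A reader might infer three stronger things.

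- *That the treatment comparison is confounded.* Treatment is randomised, so the omission is mainly a matter of precision. The per-protocol and MITT-narrow sets drop some switchers and could introduce imbalance, but the documents give no switcher counts, so this cannot be sized.
- *That the trial is short of its stated power.* Step 1 shows that it is not.
- *That prior prolapse surgery should simply go in as yes/no.* Protocol B.3 and the note to E.2 accept women whose earlier repair is unknown, so this covariate needs a rule for unknown status.

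Timing also matters. SAP section 12 (Version 2) reports events by arm after year 3. Replacing the primary model after unmasking would be post hoc.

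**Conclusion.** The point holds as a modest precision issue and a wording error. SAP 9.4.2 claims more adjustment than it specifies, and no planned analysis of the primary outcome uses baseline prolapse extent.

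Under the planned effect, adjustment is worth about 0 to 2 points of power for H2 and H3 at assumed binary HRs of 1 to 2, and about 5 points at HRs of 3 and 2. A strong continuous predictor gives a similar 3 to 5 points. The gain is up to about 6 points if native tissue does better than planned. It is nil for H1, and the cost is about 0.1 point if the covariate has no effect. The size rests entirely on assumed prognostic strengths and prevalences. In step 2 the gain comes from both covariates together, so prolapse extent alone would give less there.

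**What to change.** **If data are still masked:**

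- Add baseline maximum prolapse extent (largest of Ba, Bp and C, continuous) to the primary PWE model alongside pooled site and age category.
- For the yearly failure probabilities, state whether the covariate is set at its overall mean or averaged over.
- Keep the 1.93 margin.
- Keep the site-and-age model as a sensitivity analysis.
- Add prior prolapse surgery only with a stated category for unknown status.

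**If data are unmasked**, as the arm-level counts in SAP section 12 suggest:

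- Leave the prespecified primary model in place.
- Add the adjusted model as a labelled sensitivity analysis.
- Reword 9.4.2 to say that the model adjusts for the stratification factors, and align the matching remark about confounders in the nonparametric section of 9.4.3.

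The cost is SAP wording, one model term and one extra table. No new data are needed. The small downside is an HR conditional on one more covariate.
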